Potential participants will be identified by reviewing Weight Watchers on line member records using our eligibility criteria of initial BMI upon entry into the program, pounds lost in the last 4-6 months, and member opted in for communications from Weight Watchers about research studies. Weight Watchers will facilitate communication to these members using existing communication channels (email). Potentially eligible individuals will be invited to visit the Way to Health portal, an NIH-funded web-based infrastructure based at the University of Pennsylvania that is used to run behavioral economic intervention studies. Participants meeting the inclusion criteria will be randomized to one of the 2 study arms through the Way to Health platform. We will use permuted block randomization with variable block sizes. Participants are randomized in a 1:1 ratio to the intervention or control arm and randomization will be stratified by: (1) sex and (2) amount of weight lost within first 4-6 months of Weight Watchers membership (<30 lbs. versus 30+lbs), as baseline weight loss may moderate treatment effects. Prior to a participant signing the informed consent, both the participant and the study coordinator will be blinded to what their potential group assignment of the participant would be if enrolled. Once consented and enrolled, neither the participants nor the study coordinator will be blinded to condition assignment due to the nature of the interventions. However, the consent form will not elucidate the design of the two intervention arms so that participants are not aware of the comparisons being made. For scientific purposes to establish valid measures of the effects of the various kinds of incentive plans, blinding participants to the overall study design is necessary, presents no increment of risk, and doesn't violate subject rights. Once a subject has been assigned to a study arm, she will receive an automatically-generated email notification about group assignment and next steps. At the close of the study, all participants will receive a debriefing letter disclosing all study arms and informing participants of the final results of the study (using de-identified data) that will be submitted for publication to an academic journal at the completion of the analysis.

Administration of Surveys and/or Process

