Basic demographic data (BMI, gender, race, education, income, household size), physical activity data (IPAQ long), and eating behavior questions (TFEQ) and 2 questions measuring delayed gratification will be collected upon enrollment. We will also collect this data, minus the demographic questions, at 6 and 12 months.

Protocol

Abstract

Obesity is the second leading cause of preventable death in the United States, (1) associated with high blood pressure (BP), type 2 diabetes, coronary heart disease, and osteoarthritis. Identifying effective strategies for treating obesity is both a clinical challenge and a public health priority. Over 70% of the U.S. population is overweight or obese, and obesity in middle age translates into higher rates of hospitalization, Medicare expenditures, disability, and mortality risk in subsequent years. While a variety of approaches are successful in achieving initial weight loss, techniques for maintenance of initial weight loss have largely been unsuccessful.

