Our previous work examining the impact of different degrees of cost sharing on employee participation, engagement, and ongoing weight loss showed that among Weight Watchers members who had initial success in losing at least 5% of their initial body weight, the majority regained weight over the subsequent 6 months; Weight Watchers members in general were at high risk of dropping out of the program altogether perhaps due to lack of success in losing weight and keeping it off (John et al 2015). Research has shown that the frequency of self-weighing is important for both prevention of weight gain and weight loss (Wing et al NEJM 2006; 355:1563-1571; Linde JA et al Ann Behav Med 2005; 30: 210-216). This study will build on our successful efforts using incentives for weight loss to test scalable ways of increasing the frequency of self-weighing among Weight Watchers members who had initial success in losing weight. This 2- arm randomized controlled trial will compare the relative effectiveness and cost-effectiveness of (1) weekly feedback without incentives to (2) weekly escalating lottery-based incentives among patients who successfully lost at least 5 kg over 4-6 months during participation in Weight Watchers (Pre Phase). Incentives will be provided to some study participants (Arm 2) for the first 6 months (Phase I), and then participants will be followed for 6 more months to examine effects following cessation of incentives (Phase II). A total of 259 participants will be randomized into the 2 arms.

Specific Aims

Aim 1: Among participants who lose 5 kg or more of baseline weight prior to randomization, assess the effectiveness of escalating lottery rewards, relative to the control group, on maintenance of weight loss over the ensuing 6 months (Phase I).

Aim 2: Assess the degree to which weight loss is maintained in the intervention group relative to usual care during the 6 months following the cessation of the interventions (Phase II).

Objectives

Overall objectives

- 1. Among participants who lose 5 kg or more of baseline weight prior to randomization, assess the effectiveness of escalating lottery rewards, relative to the control group, on maintenance of weight loss.
- 2: Assess the degree to which weight loss is maintained in the intervention groups relative to usual care during the 6 months following the cessation of the interventions (Phase II).

Primary outcome variable

Pounds of weight lost at the end of 6 months

Secondary outcome variables

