To enhance retention, we will provide a total of \$100 to participants in all arms. Participant compensation will be independent of degree of weight loss and randomization group as follows: \$50 for completing an online survey at the end of month 6 and at the end of month 12. All participants will also receive a free scale (value \$179). All payments will be approved electronically from the Way to Health platform. Payment information will be sent to Wells Fargo to process and sent to participants via check. Participants will receive an automated message from the Way to health platform notifying them of compensation after completing each required survey. Participants in the financial incentive arm of the study will receive additional payments based on their adherence to daily weighing at home as outlined below in Study Procedures.

Statistical Methods

Sample size justification

We have designed the study with adequate power to detect differences in maintenance of initial weight loss. Our intervention should achieve its maximal impact in maintaining initial weight loss at the end of Phase I, when the incentive payments cease. The primary analysis will be an intent-to-treat analysis that compares the weight loss at 6 months between the lottery and control arms, using a t-test at the 0.05 level for significance. Assuming 20% missingness, a 5 kg (11 lb) SD for weight change at 6 months, and at least 5 lb more weight loss for the intervention arm compared to control at 6 months, we will have at least 90% power to detect the improvement in our primary outcome.

Analytic approach

Primary and key secondary outcomes

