The trend over time for the frequency of at-home weight measurements will be compared between arms using a generalized estimating equation (GEE) with an autoregressive (AR-1) working correlation model; specifically the mean number of days out of 7 is modeled and compared among study arms adjusting for study week and a week-by-arm interaction. Separate models will be fit for Phases 1 and 2. A linear mixed effects model with random intercept and slope for week will also be considered. An overall average weekly frequency of weighing in will be compared between arms for Phase I and Phase II using a similar GEE approach.

Additional secondary analyses include a between-arm comparison of the percent of individuals who maintained their weight (defined as gaining no more than 1.36 kg or 3 lbs) at 6 and 12 months. We will consider whether the amount of weight gain is correlated with the average number of times per week participants weighed themselves in a cross-sectional analysis at 6 and 12 months. Comparisons will also be made of the changes in self-reported physical activity and the three domains of eating behaviors (cognitive restraint, uncontrolled eating, emotional eating) at 6 months and 12 months after initial weight loss. Descriptive analyses will be done to examine the proportion of the time people fall off the lottery escalation ladder and the number of resets to beginning for the lottery incentive arm. All secondary analyses will follow in a manner similar to the primary analysis, considering both an unadjusted and adjusted approach. Imputation models for the secondary outcomes will include as predictors the baseline value for that outcome and the other baseline covariates considered for the imputation strategy A model, as described above. For secondary outcomes with < 10% data missing data, only a single imputation strategy (imputation A) may be considered.

Exploratory Analyses

We will summarize the frequency of the self-reported weights in Phase I and Phase II and examine whether there will be a difference by arm. We will further explore intervention effects and examine whether there may be a potential interaction between the baseline delayed gratification score and treatment arm.

Study Procedures

Procedures

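### The trial pays for self-weighing but, in the text supplied, records no self-weighing frequency before randomization; one survey question would supply a baseline covariate and a moderator

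*Combined protocol and SAP*

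**What the plan says.** The Abstract says that the study will "test scalable ways of increasing the frequency of self-weighing among Weight Watchers members who had initial success in losing weight", and rests this on research that "the frequency of self-weighing is important for both prevention of weight gain and weight loss". Under Procedures, a lottery-arm participant qualifies each week by weighing on 6 of 7 days. Under Design, both arms are asked to meet that target, and under Subject recruitment everyone receives a free scale.

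The enrollment data are "Basic demographic data (BMI, gender, race, education, income, household size), physical activity data (IPAQ long), and eating behavior questions (TFEQ", followed by two questions on delayed gratification. The activity, eating and gratification items are repeated at 6 and 12 months.

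Average weigh-in frequency in Phases I and II is secondary outcomes 3 and 4; its linear trend is outcomes 5 and 6. For missing data, Analysis of other outcomes states: "Imputation models for the secondary outcomes will include as predictors the baseline value for that outcome", together with the Imputation A covariates. Exploratory Analyses plans one moderator analysis, arm by baseline delayed gratification, and summarizes the frequency of weights self-reported online in Phases I and II only.

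**The concern.** The plan takes a baseline reading of the behaviors it follows as side outcomes, activity and eating, but not of the one it pays for. A person who weighed once a week before entry and a person who weighed daily look the same in the data set, although the lottery would have to work differently in each: by raising weighing in the first and by keeping it up in the second.

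At stake are the precision of the weigh-in comparisons, a predictor for imputing them, and any view of effect by prior habit. Recall collected after randomization could be colored by the assigned arm, so the item is best taken at enrollment.

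**Working it through.** **1. Where a baseline weighing frequency could appear**

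| Place in the plan | Content | Prior self-weighing? |
|---|---|---|
| Key inclusion and exclusion criteria | age, BMI, loss of at least 5 kg, stable health, online membership; exclusions | no |
| Administration of Surveys and/or Process | demographics, IPAQ, TFEQ, delayed gratification | no |
| Method for Assigning Subjects to Groups (strata) | sex; prior loss under 30 lb or 30 lb and over | no |
| Adjusted model | baseline weight, age, sex, race, BMI, education, income, MET-minutes | not listed |
| Imputation A | similar baseline items plus eating and gratification scores | no |
| Exploratory Analyses (moderator) | delayed gratification | no |
| Screening questionnaire (Procedures) | described as documenting previous weight loss | form not supplied |

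**2. Can it be recovered later?** Under Procedures, participants learn their arm immediately after randomization, and scale weighing is described after that step. Scale data, as described, are therefore post-randomization. Program weight logs might reach back before entry, but the plan uses them only for Phases I and II.

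**3. Room to increase.** With b days per week at baseline, the rise needed to qualify is 6 − b. For b = 1 it is 5 days; for b = 6 or 7 there is none. This limits increase. It does not limit prevention of decline.

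**4. The plan's power figure.** Inputs: "A total of 259 participants will be randomized into the 2 arms"; "Participants are randomized in a 1:1 ratio to the intervention or control arm"; "using a t-test at the 0.05 level for significance" (sidedness not stated, two-sided assumed); "Assuming 20% missingness, a 5 kg (11 lb) SD for weight change at 6 months"; difference 5 lb.

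- Evaluable per arm: 259 × 0.80 / 2 = 103.6.
- Standard error: 11 × √(2/103.6) = 1.528 lb.
- Noncentrality: 5 / 1.528 = 3.27.
- Power: 90.3% by noncentral t (90.5% by the normal approximation), against at least 90% stated. It reproduces, with little slack.

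**5. Illustration only.** Let a share f of entrants have zero response; the documents give no f. There are two ways to read the 5 lb. If it is the effect in the remainder, the average is 5(1 − f). If it is the average over everyone randomized, the remainder needs 5/(1 − f) and power stays at 90.3%.

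| f | Average effect if the remainder gains 5 lb | Power | Remainder's effect if 5 lb is the overall average |
|---|---|---|---|
| 10% | 4.5 lb | 83% | 5.6 lb |
| 20% | 4.0 lb | 74% | 6.3 lb |
| 30% | 3.5 lb | 63% | 7.1 lb |
| 40% | 3.0 lb | 50% | 8.3 lb |
| 50% | 2.5 lb | 37% | 10.0 lb |

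**6. What an interaction on weight could show.** Assume an even split by baseline weighing. Each subgroup difference has standard error 11 × √(2/51.8) = 2.16 lb, and their contrast √2 × 2.16 = 3.06 lb. At the same noncentrality, about 90% power needs a contrast of 3.27 × 3.06 = 10 lb. On weight, the interaction is descriptive.

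**The case against.** A reader might go further and infer that near-daily weighers cannot respond, that they dilute the effect so that the trial is underpowered, and that a null weight result could not be interpreted. The documents do not support these readings.

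- *Cannot respond.* This is a maintenance trial. The Abstract reports that most successful members regained weight over the next 6 months. A daily weigher can lapse over 24 weeks, and the lottery penalizes lapsing by sending a participant who misses the target back to the start of the schedule, with one exception. The between-arm comparison of weighing trend would pick this up.
- *Dilution and power.* The 5 lb in Sample size justification is a difference between arms, so it is an average over all randomized and may already include people with little room to increase. The share f and the zero response are both assumed.
- *Enrichment for frequent weighers.* The Abstract links self-weighing to weight loss but gives no frequency for eligible members. Enrichment is plausible, not shown.
- *Unreadable null.* Control-arm scale data show weighing under trial conditions, and the weigh-in comparisons are prespecified. If both arms sit near 6 of 7 days, a ceiling is the likely explanation; if weighing separates and weight does not, more weighing did not help.

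It is also fair that outcomes 5 and 6 are within-phase slopes with no natural baseline value, and that the text does not say whether a week without scale data counts as zero or as missing, so the imputation gap may be small in practice.

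What this leaves untouched: control-arm data give a group-level picture in people who have been given a scale, a goal and weekly feedback. They do not show prior habit, and they cannot identify which lottery-arm participants entered already at goal.

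**Conclusion.** The gap is real and modest. In the text supplied, no self-weighing frequency is recorded before randomization. Outcomes 3 and 4 therefore lack the baseline value that the plan's imputation rule calls for, and effect by prior weighing cannot be examined. The primary intent-to-treat comparison is unbiased and its stated power is correct on its own inputs.

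The size of the benefit cannot be computed from the documents. To a linear approximation, adjusting for a baseline with correlation r to average weigh-in frequency cuts residual variance by the factor 1 − r², and r is not given. A gain is likely, because past weighing is a natural predictor of later weighing.

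One reservation applies: the screening questionnaire may ask about weighing. If it does, what is missing is the use of the answer, since no listed analysis includes it.

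**What to change.** Before randomization, add one survey question: on how many days per week did you weigh yourself over the past month? If the program can supply pre-randomization weight logs, use them as a second source. Then:

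- add the variable to the adjusted versions of the Phase I and Phase II weigh-in models and to the adjusted weight model;
- add it to Imputation A;
- add an exploratory arm-by-baseline-weighing interaction beside the delayed-gratification one, labeled descriptive for weight.

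Eligibility, sample size and the unadjusted primary t-test stay as they are, so the change does not alter the power of the primary test. The cost is one survey item and a few words of analysis plan. Asking may slightly prompt weighing, but equally in both arms because it precedes randomization.

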The primary analysis will be an unadjusted between-arm comparison of the change in weight from baseline (randomization) to 6 months, using a t- test performed at the 0.05 significance level. The primary analysis will be done as an intent-to-treat (ITT) analysis, including each participant in the group to which she was randomized, regardless of adherence to the assigned intervention. The 6-month weight is determined as the first weight that is inside the 6-month visit window. A multiple imputation strategy based on baseline covariates (including study arm) will be used to fill in the missing data for the primary outcome. For more details see multiple imputation strategy below. A complete case analysis will be done as a sensitivity analysis. A second sensitivity, assuming weight returned to baseline (weight at time of randomization) may also be considered. We will also estimate the difference between arms at 6-month in an adjusted analysis where the change from baseline is regressed in a linear model on study arm, baseline weight, and other covariates including age, sex, race, BMI, education, income, and physical activity (total MET-minutes/week).

Analyses of the key secondary outcome, weight change between baseline and 12 months (Phase 2) will be conducted in a similar manner as the primary outcome. The 12-month weight is determined as the weight that is the first weight inside the 12-month visit window. The multiple imputation algorithm for the 12-month outcome will additionally consider the 6-month weight outcome as an additional predictor, using a chained imputation type approach.

Multiple Imputation Strategy

Missing primary outcome data, weight at 6 months, will be imputed using baseline covariates only (Imputation A); variables include age, sex, race, weight, BMI qualifying weight loss, education, income, IPAQ activity level, MET-minutes walking, the three domains of eating behaviors (cognitive restraint, uncontrolled eating, emotional eating, and two scores related to delayed gratification behavior. A supportive analysis will also be done also using post-randomization variables (Imputation B); these variables include the most recent logged weight and time since last weight, The imputation strategy for the weight at 12 months and other secondary outcomes will proceed in a similar manner. Weight at 12 months will additionally use the 6-month weight outcome, using chained imputation approach (1).

Analysis of other outcomes

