Potentially eligible patients will be sent emails directing them to the Way to Health website. Participants will be required to sign up online and complete the screening questionnaire where they will be asked to document their previous weight loss. The screening questionnaire has been attached.

Participants will be asked to electronically sign the consent and complete the demographic survey on the platform. Participants will then be randomized to one of two study arms. Immediately following randomization, each participant will receive a description of her assigned treatment condition by email and on the study websites dashboard (See Control and Escalating Lottery dashboard instructions attached). Participants will self-monitor their weights daily. Every day, at a time convenient for the participant, participant will weigh themselves using the internet-enabled scale. The scale will wirelessly transmit their weight data where it will be stored on the Way to Health portal. Each week, subjects will be text paged with feedback on their progress relative to their weekly goal. Participants in the escalating lottery arm will be eligible for a weekly lottery with an expected value of \$3.98 in week 1 that will increase by \$0.43 per week if, prior to resolution of the lottery, they weighed in 6 out of 7 days the prior week. If participants in the escalating rewards arm miss the target in a given week, they will go back to the beginning of the escalating rewards schedule, with one exception: participants will be given the opportunity to return to their previous place in the schedule if they meet goals the following week.

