The lottery provides both infrequent large payoffs (a 1 in 100 chance at a \$110 reward in week 1) and frequent small payoffs (an 18 in 100 chance at a \$16 reward in the week 1) since subjects are motivated by both the future (fixation on large potential winnings) and the past (how often did I win?). Participants in the lottery arm will be asked to pick a 2-digit number upon entry into the study, e.g. 27. A two digit random number will be generated for each week. If the random number includes one digit, either a 2 or 7 in the same position as the participant's number (an 18 in 100 chance), and the subject weighed in at least 6 days that week, s/ he wins a small reward. If the random number matches 27 exactly (a 1 in 100 chance) the subject wins the large reward. When a subject does not meet their goal of weighing in 6/7 days in a week, we will still generate a 2-digit daily number and tell the subject if s/he would have won the lottery that week if s/he had weighed in at least 6 out of 7 days. We believe that a desire to avoid the regret associated with not winning combined with learning that one would have won, had one been adherent, will motivate participants to a greater degree than only on

the value of the rewards. Other than the total number of lottery weeks (24), there is no limit to the number of times a person could win the daily lottery if their number comes up; however, for participants who make all of their weekly goals for the entire 6 months (24 weeks) of the intervention, the expected value of the lottery is approximately \$214.

All participants will be required to complete online surveys at months 6 and 12. Participants will receive automated emails/text messages from the Way to Health platform notifying them of their compensation payment for completing each of the required surveys at months 6 an 12. Participants will receive \$50 for surveys at months 6 and 12. All payments will be approved electronically from the Way to Health platform. Payment information will be sent to Wells Fargo to process and send to participants via check every week. Between months 7-12 (Phase II), participants will not receive incentives tied to weighing in to evaluate sustainability of effects achieved in Phase I.

Subject Privacy

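### The month-6 payment is earned by the survey alone, so a paid participant can lack the primary-outcome weight; a same-day weigh-in prompt in both arms would be a cheap improvement

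*Combined protocol and SAP*

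**What the plan says.** **Payment.** The compensation paragraph under Subject recruitment gives every participant $50 "for completing an online survey at the end of month 6 and at the end of month 12", for the stated purpose of improving retention and regardless of arm or weight loss. Procedures repeats the survey condition: "All participants will be required to complete online surveys at months 6 and 12". Neither place mentions a weight.

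**Primary outcome.** Under Primary and key secondary outcomes: "The 6-month weight is determined as the first weight that is inside the 6-month visit window". The window is not given in days. Procedures describes home weighing on an internet-enabled scale: "The scale will wirelessly transmit their weight data where it will be stored on the Way to Health portal".

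**Survey content.** Administration of Surveys and/or Process lists activity, eating-behavior and delayed-gratification questions for months 6 and 12. The demographic block, where BMI sits, is not repeated, so no weight item is described.

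**Who is paid to weigh.** Only the incentive arm receives "additional payments based on their adherence to daily weighing at home". Both arms get a free scale, weekly tips and weekly feedback, and both are asked to weigh on 6 of 7 days.

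**Missing weights.** The primary imputation uses baseline covariates and study arm. A supportive Imputation B adds post-randomization data: "these variables include the most recent logged weight and time since last weight". A complete-case analysis is planned, and an analysis that sets weight back to its randomization value may be considered.

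**The concern.** The retention payment secures the survey and leaves the primary outcome to routine home weighing. In this trial weighing is also the behavior that one arm is paid for, so the chance of having a month-6 weight could depend on arm. The Abstract's rationale is that frequent self-weighing helps prevent weight gain. On that premise, people who stop weighing may have regained more than those who continue.

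The primary imputation fills a missing weight from participants in the same arm with similar baseline data. It carries over the regain of those observed and cannot see regain that happened later and led someone to stop weighing. What is at stake is possible bias in the primary contrast, of unknown sign, rather than lost power.

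**Working it through.** **1. The plan's own figure.** Inputs from Sample size justification: SD 11 lb, difference 5 lb, 20% missing, t-test at 0.05 (taken as two-sided). With 259 randomized 1:1 there are 259/2 = 129.5 per arm, and 129.5 × 0.80 = 103.6 observed. The standard error is 11 × √(2/103.6) = 1.528 lb and the noncentrality is 5/1.528 = 3.27. Power from the noncentral t is 90.25%, against a stated figure of at least 90%. It reproduces.

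**2. Unequal capture alone.** Assume 15% missing in lottery and 25% in control, still 20% overall. Then n = 110.1 and 97.1, the standard error is 1.531 lb and power is 90.1%. Unequal numbers by themselves cost almost nothing.

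**3. Unequal capture with regain that the imputation cannot see.** Let m be the fraction missing in an arm and g the extra gain of its missing participants over those observed. Imputing the observed mean understates that arm's gain by m × g. Shift against the lottery = (control m × g) − (lottery m × g). All m and g below are assumed; the documents give neither by arm.

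| Extra gain, lottery / control (lb) | Shift against the lottery (lb) | Consequence |
|---|---|---|
| 5 / 5 | 0.25×5 − 0.15×5 = 0.50 | contrast 4.5 lb, power 83.3% |
| 5 / 3 | 0.75 − 0.75 = 0 | none |
| 5 / 0 | 0 − 0.75 = −0.75 (toward the lottery) | with no true effect, chance of a significant lottery benefit is 7.0% instead of 2.5% |

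The sign depends entirely on inputs that the documents do not supply.

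**4. What recovering weights would do (5 / 5 case).** Suppose a fraction r of the missing is recovered, as a random sample of the missing. Recovered people join the observed group and move its mean, so the remaining understatement in an arm is m × g × (1 − m)(1 − r) / (1 − m + r × m).

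- r = 0 in both arms: 1.25 − 0.75 = 0.50 lb.
- r = 0.25 in both: control 1.25 × 0.75 × 0.75/0.8125 = 0.865; lottery 0.75 × 0.85 × 0.75/0.8875 = 0.539; shift 0.33 lb.
- r = 0.50 in both: control 1.25 × 0.75 × 0.50/0.875 = 0.536; lottery 0.75 × 0.85 × 0.50/0.925 = 0.345; shift 0.19 lb.
- r = 0.50 in lottery only: 1.25 − 0.345 = 0.91 lb. Lopsided recovery makes the shift larger.

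**5. Effect on the weighing-frequency outcomes.** One extra weigh-in over the 24 lottery weeks adds 1/24 = 0.042 days per week to a participant's average. Over 26 weeks of Phase II it adds 1/26 = 0.038.

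**The case against.** The strongest reply is that the plan already allows for this. It budgets 20% missingness, needs only one weight in the window, asks both arms to weigh 6 days in 7 with weekly feedback, and adds Imputation B, a complete-case analysis and possibly a return-to-baseline analysis. The survey and dashboard instructions are attachments that are not shown, so a month-6 prompt or a weight item may already exist.

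Much of that stands, and it is why this is a suggestion only. The planned analyses help in part. Imputation B uses later weights but is supportive. The complete-case analysis rests on the same observed participants. The return-to-baseline analysis assigns zero change since randomization and is optional.

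Three stronger readings are tempting, and the documents support none of them.

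- *A reader might infer that the power is overstated.* It reproduces, and unequal capture alone leaves it at 90.1%.
- *A reader might infer that the result is biased in a known direction.* No capture rate or regain by arm is given, and plausible inputs produce a shift either way or none.
- *A reader might infer that the $50 should depend on a weigh-in.* That would pay control participants to weigh in a trial of paying people to weigh. It could also conflict with the rule in Design and Procedures against incentives tied to weighing in months 7-12: the window is not given in days, and Procedures equates the 6-month intervention with 24 weeks, so a weight after week 24 may already fall in Phase II.

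**Conclusion.** The point holds as a cheap, optional improvement and not as an error. As the text describes the payment and the survey, a participant can satisfy the month-6 payment condition without supplying the primary outcome, and only one arm has a financial reason to weigh. Whether this produces any bias, and in which direction, cannot be determined from the documents.

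The figures of 0.50, 0.33 and 0.19 lb rest on assumed missingness of 15% and 25%, an assumed 5 lb excess gain in both arms, and recovery that is random among the missing and equal across arms. They show scale and are not estimates. More real weights reduce reliance on the imputation model, but bias falls reliably only if recovery is similar in the two arms. Confidence is medium, because the attachments are not shown.

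**What to change.** Apply both steps identically in the two arms.

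1. Have the month-6 survey page and its reminder ask for a scale weigh-in that day, timed to fall inside the 6-month window. This step can add primary-outcome weights.
2. Add a self-reported current weight item to the 6- and 12-month surveys, for use as a predictor in supportive Imputation B only. The primary analysis does not change.

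Leave the $50 rule as it is. Report the proportion with a 6-month weight by arm, so that lopsided capture is visible. If the attached survey or dashboard instructions already contain such a prompt, saying so closes the point.

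**Cost.** One line of text on the survey page and in its reminder, and one survey item. The platform already automates participant messages ("Participants will receive an automated message from the Way to health platform notifying them of compensation after completing each required survey"). No extra money or visits are needed.

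**Downsides.** The prompt reaches only people who respond to the survey or its reminder, and the overlap between survey non-response and missing weights is not given. If follow-up has begun, it reaches only those not yet at month 6. The prompted weigh-in adds about 0.04 days per week to the average weighing frequency of a participant who responds to it.
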